Person-to-person transmission: We will use the CDC definition for influenza transmission that refers to the ability of an influenza virus to spread from one person to another, most commonly through large or small droplets containing influenza virus that are expelled when a sick person is coughing or sneezing.

XI. Statistical Analyses

The primary objective is to precisely estimate the proportion of drug eligible individuals with an influenza diagnosis who initiate treatment within 48 hours. We define precision in terms of the width of a 95% confidence interval. The width of a 95% CI will be less than or equal to $\pm 1.96 \cdot 0.5/\sqrt{n}$ where n is the number of individuals who test positive for flu. With 250 households participating and an attack rate of 25% we expect 63 individuals with confirmed influenza infection. This will give a 95% CI for the proportion initiating treatment of ± 0.12 or less.

The proportion of drug eligible individuals receiving the drug and initiating treatment within 48 hours of symptom onset using home-based self-test and delivery methods will be estimated. Binomial regression with log link will be used to calculate the relative risk of receiving and initiating treatment within 48 hours by demographic and clinical factors, including age, sex, race/ethnicity, symptom types, symptom severity, and duration of symptoms. The RR, 95% confidence intervals and p-values will be reported.

For the secondary endpoints of symptom duration and severity, drug eligible and drug ineligible participants will be analyzed separately. Symptom severity will be measured on a 4-point scale (0 = no symptoms, 1 = mild, 2 = moderate, 3 = severe) for each influenza-associated symptom the participant reports experiencing. Influenza-associated symptoms the participant does not report as experiencing will be coded as 0. An additional analysis will be conducted comparing secondary endpoints for drug eligible, influenza-infected study participants that received and initiated treatment within 48 hours of symptom onset and those that initiated treatment later than 48 hours. Kaplan-Meier curves will be used to present and analyze time to resolution of symptoms, defined as the time when the influenza-positive participant reports experiencing no respiratory or systemic symptoms. For study participants who received BXM, a Cox proportional hazards model will be used to calculate the hazard ratio, 95% confidence interval, and p-value for symptom duration by group (therapy within 48 hours of symptom onset, and therapy after 48 hours of symptom onset). The analysis of drug ineligible study participants will use a similar approach but will cluster by household and use a robust variance for computing confidence intervals and p-values. For BXM recipients, symptom severity will be compared between groups (therapy within 48 hours of symptom onset, and therapy after 48 hours of symptom onset) using proportions for categorical measures of severity and Pearson's chi-square test, as well as using ordinal regression. As above, the analysis using ordinal regression of drug ineligible study participants will cluster by household and use a robust variance for computing confidence intervals and p-values.

For the secondary endpoints of maximum viral titer and duration of viral RNA detection, we will use t-tests or nonparametric alternatives and linear regression to assess maximum viral titer and Kaplan-Meier curves and Cox proportional hazards models to assess duration of viral RNA detection.

Interim Analysis

This study is being conducted over the course of one influenza season. Therefore, an interim analysis will not be performed.

Antiviral resistance analysis

The secondary outcome data regarding emergence of BXM resistance will be reviewed at the end of the influenza season via genome sequencing of the viral RNA.

Health economic analysis

The economic analysis will include a 'within-study' cost-effectiveness analysis to compare the costs and health outcomes accrued over the follow-up period for individuals that initiated the therapy within 48 hours of symptom onset and after 48 hours of symptom onset. Results will be presented as an incremental cost-effectiveness ratio, assessed using health resource utilization and school and work absenteeism, for baloxavir treatment compared at these two time points.

Translational analysis

Samples will be sent to the central laboratory for storage and analysis. The goals of the translational research will be to determine the association between influenza infection and: (1) influenza strain (by genetic sequencing), (2) viral kinetics (maximum titer, duration viral RNA detection). It will also monitor for the emergence of antiviral resistance among strains. Additional testing and sequencing of non-influenza respiratory pathogens will also occur.

XII. End of study

The end of study is defined as when the last household has had their last data collected during the final influenza season of the study period. Active household recruitment and enrollment will take place prior to and during each annual influenza season, and the study itself will take place over the course of one influenza season: November 2019-May 2020. Overall, enrollment will begin October 2019; active participation is projected to start November 2019, and the study is projected to end in May 2020.

XIII. References

2. Putri WCWS, Muscatello DJ, Stockwell MS, Newall AT. Economic burden of seasonal influenza in the United States. *Vaccine*. 2018;36(27),3960-3966. doi:10.1016/j.vaccine.2018.05.057
3. Centers for Disease Control and Prevention. Estimated Range of Annual Burden of Flu in the U.S. <https://www.cdc.gov/flu/about/burden/index.html>. Updated February 19, 2019. Accessed July 21, 2019.

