review the participant’s medical information and provide an influenza diagnosis based on clinical judgement. If probable influenza is diagnosed, the 98point6 provider will confirm that antiviral treatment is appropriate. If appropriate, drug eligible study participant will subsequently receive a single dose of BXM delivered to their household via rapid delivery service for therapy initiation within 48 hours of symptom onset. Concurrently, the ill individual will collect a Study Day 0 nasal swab sample that will be mailed back to the laboratory for further testing. Additional nasal swabs will be collected at Study Day 2-3 and Study Day 5-7. If influenza is not diagnosed, the ill individual will provide one self-collected or parent/permanent legal guardian-collected nasal swab specimen that will be mailed back to the laboratory for further testing, and the household will remain enrolled and all study participants in the household will continue to self-monitor for presence of symptoms. Once an eligible study participant receives BXM, no additional household members will be eligible to receive BXM; the household will be able to continue monitoring for onset of symptoms, as well as self-testing and swabbing when symptoms develops, but the household will no longer be able to receive BXM delivery.

Figure 1. Study schema

Symptom Table

Feeling Feverish	Muscle or Body Aches
Headache	Rash
Sore Throat or Itchy/Scratchy Nose	Runny/stuffy nose
Feeling More Tired Than Usual	Muscle or body aches
Nausea or Vomiting	Increased trouble with breathing
Ear Pain or Ear Discharge	Diarrhea

The study is being conducted in the Seattle, WA area over one influenza season. The goal is to have 250 households comply with full study procedures. Of these, 25% are estimated to have an individual in the household diagnosed with influenza based on estimates from previous household studies.^{23, 28-29}

A table for influenza attack rates by household size is provided below.

Household attack rate	Total households enrolled	Primary cases	Secondary cases (mean household size 5)	Secondary cases (mean household size 4)	Secondary cases (mean household size 3)
25%	250	63	45-96	34-72	23-48
20%	250	50	36-76	27-57	18-38
10%	250	25	18-38	14-29	9-19
Mean household size includes case.					
Secondary attack rate 18-38%, secondary cases presented as a range based on these high and low bounds. ³⁰⁻³²					

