The University of Washington is the sponsor of the study which is supported by an anonymous funder who does not have any ownership over the management and conduct of the study, the data, or the rights to publish.

III. Objectives

The objective of the study is to measure the proportion of individuals who are initiated on antiviral therapy within 48 hours of symptom onset using a home-based self-test, followed by a telehealth consultation to diagnose influenza and home delivery of antivirals

Primary Outcome Measures

The primary outcome measure will be the proportion of eligible individuals who initiate antiviral therapy at home within 48 hours of symptom onset utilizing a home-based test and the telehealth app for influenza diagnosis and rapid home-delivery of antivirals. It will be calculated using binomial regression with log link, where the number of drug eligible influenza-diagnosed individuals, defined as the number of individuals eligible to receive BXM with both self-test positive influenza and laboratory-confirmed influenza, reporting administration of the study drug within 48 hours of symptom onset is divided by the total number of drug eligible individuals with both self-test positive influenza and laboratory-confirmed influenza.

Secondary endpoints:

- Proportion of individuals who test positive for influenza using the home-based test within 48 hours of symptom onset
- Proportion of individuals with a positive home-based influenza self-test who have a positive test confirmed by the central laboratory
- Sensitivity and specificity of a self-test compared to a laboratory-based molecular influenza test
- Proportion of individuals who are delivered antivirals within 48 hours of symptom onset
- Proportion of individuals who self-report administration antiviral therapy within 48 hours of symptom onset
- Symptom duration and severity among drug eligible and drug ineligible influenza-positive individuals
- Proportion of families with influenza infection diagnosed within 7 days of an index case (another influenza-positive household member)
- Viral quantity and duration of viral RNA detection among drug eligible and drug ineligible influenza-positive participants
- Proportion of drug ineligible study participants seeking medical care for respiratory illness symptoms
- Proportion of individuals who choose to take a self-test among those who are eligible to take a self-test

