At the start of influenza season, defined in this study as November 1, pre-enrolled households will receive weekly reminders via text message, email, or phone call to complete their symptom monitoring logs regarding the presence or absence of cough or 2 or more respiratory symptoms. Additionally, households will be reminded to self-test for influenza as soon as symptoms develop in a member of the household. The household will complete a symptom monitoring log via REDCap online or text-message, regardless of age, for the duration of the influenza season (November 1-May 1). Once a household has a drug eligible participant who is diagnosed with probable influenza by a telehealth provider and that participant has received and administered BXM, weekly monitoring will still occur, but the household is no longer eligible to receive BXM delivery.

For households that enroll during the influenza season, they will receive weekly reminders via text message, email, or phone call to complete their symptom monitoring logs starting the day of enrollment. These reminders will be identical to the reminders the pre-enrolled household receive. The household will complete a weekly symptom monitoring log via REDCap online or text-message, regardless of age, for the duration of the influenza season (November 1-May 1). Once a household has a drug eligible participant who is diagnosed with probable influenza by a telehealth provider and that participant has received and administered BXM, weekly monitoring will still occur, but the household is no longer eligible to receive BXM delivery.

Onset of Symptoms

Immediately following the onset of an acute cough or 2 or more respiratory symptoms in a drug ineligible participant, the following procedures will occur:

1. The participant will self-test for influenza using the prepositioned home-testing kit as long as the following criteria are met:
 - Symptom duration <48 hours
 - Cough present or 2 or more respiratory symptoms present
2. The individual will provide a nasal swab specimen collected via self-swab or parent/permanent legal guardian-swab, which will be mailed back to the laboratory for testing and further characterization (See VI. Laboratory Procedures section).
3. Next, the ill individual will complete day 0 of the illness questionnaire in REDCap, which will ask information about respiratory and systemic symptoms, recent travel history, and absenteeism.

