Success = Participant initiated on antiviral therapy within 48 hours of symptom onset
Failure = Participant is not initiated on antiviral therapy (**more than 48 hours** after symptom onset *or* participant **never** initiates antiviral therapy)

Table 1. Estimated secondary attack rates for planned 2019-2020 study aim on household transmission dynamics.

The study is being conducted in the Seattle, WA area over one influenza season. The goal is to enroll at least 250 (up to 1,000) households. Of these, 25% are estimated to have an individual in the household diagnosed with influenza based on estimates from previous household studies.^{23, 28-29}

A table for influenza attack rates by household size is provided below.

Household attack rate	Total households enrolled	Primary cases	Secondary cases (mean household size 5)	Secondary cases (mean household size 4)	Secondary cases (mean household size 3)
25%	250	63	45-96	34-72	23-48

20%	250	50	36-76	27-57	18-38
10%	250	25	18-38	14-29	9-19
Mean household size includes case.					
Secondary attack rate 18-38%, secondary cases presented as a range based on these high and low bounds.³⁰⁻³²					

Incidence Density

Using time-specific variables such as date of enrollment, weekly symptom diaries and questionnaires, Incidence Density (ID) will be calculated, defined with the following formula:

Incidence Density =

Number of participants that successfully initiate antiviral therapy within 48 hours of symptom onset (among participants who have a cough and self-test positive for influenza)

Total person-days

Model

The proportion of individuals that 1) test positive and 2) receive and initiate treatment within 48 hours of symptom onset using home-based self-test and delivery methods will be analyzed with a binomial regression GLMM with a log link. The outcome follows a binomial distribution, with the number of successes in a series of n independent Bernoulli trials, where each trial has probability of success p . Successes here are defined as an individual successfully initiated on antiviral therapy within 48 hours of symptom onset using home-based self-test to diagnose influenza and home delivery of antivirals. The model is defined below:

Incidence proportions of influenza will be presented in tables.

A formal statistical comparisons between study periods (control vs. intervention) will be performed using a Wald test of the hypothesis

$H_0: RR=1$

$H_a: RR \neq 1$

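### The primary denominator does not say whether drug-eligible influenza cases arising after a household has had its one BXM course are counted; on the most natural reading they are, and they cannot be successes

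*Protocol*

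**What the plan says.** **The household rule.** Protocol II (Study design): "Once an eligible study participant receives BXM, no additional household members will be eligible to receive BXM". Follow-up of the household does not stop: "the household will be able to continue monitoring for onset of symptoms, as well as self-testing and swabbing when symptoms develops". Protocol V (Weekly Monitoring) repeats the bar with a different trigger, once "that participant has received and administered BXM, weekly monitoring will still occur, but the household is no longer eligible to receive BXM delivery".

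**The primary outcome.** Protocol III (Primary Outcome Measures) counts on-time starters among influenza-diagnosed individuals, "defined as the number of individuals eligible to receive BXM with both self-test positive influenza and laboratory-confirmed influenza". That count "is divided by the total number of drug eligible individuals with both self-test positive influenza and laboratory-confirmed influenza". Nothing there restricts the denominator to first cases, or to households that can still be supplied.

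**Who is drug eligible.** Protocol II and IV set this by age, weight and the exclusion list, as a status in which people enrol. Two other places read differently. Section IV also says that co-residents of the case, whatever their age, are drug ineligible. Section X (Definitions) describes the drug-ineligible participant simply as one who cannot receive BXM.

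**The SAP.** Section B6 has "Failure = Participant is not initiated on antiviral therapy", and this covers late starters and those who never start. Its cumulative-incidence formula, however, divides by influenza-free participants at baseline, which is not the protocol's denominator.

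**The concern.** The primary objective is to learn whether self-test, telehealth consultation and rapid delivery get treatment started within 48 hours. A confirmed case to whom the protocol itself declines to send drug carries no information on that. If such cases are counted, the estimate falls by an amount set by household size, the number of eligible members and the secondary attack rate, none of which is delivery performance.

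The documents do not settle whether they are counted. If the choice is left until the data are in, the headline proportion depends on a decision taken after the result is visible. The opposite reading has its own cost: adolescents and adults who enrolled as drug eligible would pass mid-season into the drug-ineligible group, which section XI analyses separately for symptom duration and severity.

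BXM is prescribed on the provider's judgement of probable influenza, so an illness that proves not to be influenza can also use the household's course. A true case later in that household meets the same problem. The documents give no figure for how often this would happen.

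**Working it through.** **The protocol's own figures reproduce.**
- Affected households: 250 × 0.25 = 62.5, given as 63.
- Half-width: 1.96 × 0.5/√63 = 0.1235, given as ±0.12.
- Secondary cases at household size 4: 63 × 3 × 0.18 = 34.0 and 63 × 3 × 0.38 = 71.8, given as 34-72.

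The precision statement therefore uses one case per affected household, although section XI describes n as individuals who test positive.

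**Ceiling if barred cases are counted.** Assumptions:
- Every affected household has 4 members, k of them drug eligible. The documents give only the minimum, k = 2.
- The first case is equally likely to be any member. Each other member is infected with probability s.
- Every case is self-test positive and laboratory-confirmed. Every case that may be supplied is treated on time.
- Cases occur one after another, so only the first eligible case is supplied.

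Per affected household:
- Expected eligible cases: E = k(0.25 + 0.75s)
- Probability of at least one eligible case: P = 1 − (1 − k/4)(1 − s)^k
- Ceiling = P/E; barred cases = 63(E − P)

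Worked example, k = 2, s = 0.18: E = 2 × 0.385 = 0.770; P = 1 − 0.5 × 0.82² = 0.6638; ceiling = 0.862; barred = 63 × 0.1062 = 6.7 of 48.5.

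| s | k = 2 | k = 3 | k = 4 |
|---|---|---|---|
| 0.18 | 86.2% (6.7 of 48.5 barred) | 74.6% (18.4 of 72.8) | 64.9% (34.0 of 97.0) |
| 0.38 | 75.5% (16.5 of 67.4) | 58.6% (41.9 of 101.1) | 46.7% (71.8 of 134.8) |
| 0.136 | 89.0% | 79.4% | 71.0% |
| 0.019 | 98.2% | 96.4% | 94.6% |

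The first two rows use the protocol's planning range for the secondary attack rate. The last two use the rates cited in section I for contacts of index patients given placebo (13.6%) and BXM (1.9%). The last row is a favourable case for k below 4, because it applies 1.9% even when the first case is drug ineligible and untreated. The general 18-38% errs the other way if BXM lowers transmission.

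**If barred cases are excluded.** About one eligible case per affected household remains and the ceiling is 100%. With k = 4 this is n = 63 and half-width 0.1235, the protocol's own figure.

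**The case against.** The strongest reply is that the documents can be read so that barred members are never in the denominator. Section III speaks of individuals eligible to receive BXM, and the section II rule uses the same expression to say that other household members no longer are. Section IV's sentence on co-residents of any age and the section X definition point the same way. So does sizing on 63, the primary-case count, and so does specifying household clustering only for drug-ineligible participants.

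This stands as a possible reading, but not as the better one. Section IV uses the same expression for the household entry requirement of two eligible members, where it can only mean enrolment status. Section II has people enrol as drug eligible and describes the ineligible as those who do not meet BXM criteria.

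A reader might go further and infer that the design itself caps the result well below 100%, with the SAP expressly scoring barred cases as failures. The documents do not support that. The SAP's failure definition sits with a different denominator, in a plan that predates protocol version 3.1 and never mentions the one-course rule. The protocol does not say that 18-38% applies once a member has taken BXM, and at 1.9% the loss at size 4 is about 2 to 5 points. Nor is it exact that only one member can ever be treated: the bar starts at receipt, or at receipt and administration, so two members ill together might both be supplied first. Such overlap would raise the ceilings above.

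**Conclusion.** The point holds as a gap in the definition of the primary denominator. The household rule and the continued testing are explicit, the denominator carries no matching restriction, and the most natural reading counts cases that cannot succeed.

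Under the stated assumptions at size 4, the ceiling runs from about 86% to 47% at the planning attack rates, 89% to 71% at 13.6%, and 98% to 95% at 1.9%. At the planning rates every loss exceeds the intended ±0.12; at 1.9% none does. The eligible share of household members is not given, so no single figure can be defended.

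It would also go too far to say the primary hypothesis must fail with perfect delivery. It asks for a large percentage and sets no threshold. For a single-group pilot whose delivery log will identify the affected cases, this should be fixed by clarification before analysis; it does not invalidate the design.

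**What to change.** In Protocol III and XI and SAP B6:
- Define the primary denominator as illness episodes in enrolment-defined drug-eligible participants, self-test positive and laboratory-confirmed, with symptom onset before the household's BXM bar took effect.
- Report barred cases as a separate count, and give the all-cases proportion as a sensitivity result.
- Flag cases whose household became barred between onset and consultation, and show the primary result with and without them. An onset cut-off alone still leaves these as unavoidable non-successes.
- Keep barred members out of the drug-ineligible group in the symptom and virus analyses.
- Replace the SAP's baseline at-risk denominator so that the two documents agree.

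Sections II and V must be reconciled on whether receipt, or receipt and administration, starts the bar, because denominator membership depends on it. No change to the dispensing rule is proposed.

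The cost is wording only; the delivery log and recorded ingestion times supply the dates. The denominator shrinks and the interval widens. At s = 0.18 the maximum half-width goes from 0.98/√48.5 = 0.141 to 0.98/√41.8 = 0.152 with two eligible members, and from 0.98/√97.0 = 0.100 to 0.98/√63 = 0.123 with four.

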4. Additionally, one week later, the ill individual will complete day 7 of the illness questionnaire, which will ask information about respiratory and systemic symptoms, recent travel history, and absenteeism in 7 calendar days following the onset of a cough in the ill participant.

Immediately following the onset of an acute cough or 2 or more respiratory symptoms in a drug eligible participant, the following procedures will occur:

1. The person will self-test for influenza using the prepositioned home-testing kit as long as the following criteria are met:
 - Symptom duration <48 hours
 - Cough present or 2 or more respiratory symptoms present
 - i. Qualification for receipt of study drug will be determined based on a review of medical information with the tele-health provider. If the individual meets the required criteria (symptom duration <48 hours) and is diagnosed with probable influenza by a healthcare provider, this will trigger subsequent delivery of the intervention, if deemed appropriate.
2. Next, the ill individual will collect a nasal swab sample via self-swab or parent/legal guardian-swab as soon as possible. These specimens will then be packaged and shipping back to the laboratory via a delivery service for testing and further characterization. Additionally, the ill individual will complete day 0 of illness questionnaire in REDCap, which will ask information about respiratory and systemic symptoms, recent travel history, and absenteeism.
3. Concurrently, the participant will connect with a provider via the tele-health app previously downloaded on their smartphone. The provider will review the participant's symptoms and determine whether influenza infection is likely to be the underlying cause of the symptoms. If probable influenza is diagnosed, the tele-health provider will prescribe a weight-based dose of BXM. If antiviral treatment is not deemed appropriate by the tele-health provider, this information will be documented in the post-visit Care Plan for the study participant and subsequently shared with the study team.
4. Next, the study pharmacy will be notified that the participant is being prescribed BXM.

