If the adverse event is considered by the medical expert team to be minor in severity, it will be logged in the centralized data capture system and a summary of such events will be reported to the DSMB. If the severity of the adverse event is considered to be moderate or severe by Principal and Co-Principal Investigators, it should be reported to the safety officer (DSMB) and the cognizant IRB immediately. All study-related SAEs will be reported to the IRB within 14 days.

The following are a list of anticipated and unanticipated adverse events we expect to be attributable to the study procedures or the intervention:

Anticipated Events: Mild-moderate systemic reactions, these include diarrhea, bronchitis, nausea, nasopharyngitis, and headache.

Unanticipated Events: By definition these are unexpected in terms of their nature, (see above for anticipated events) severity, and frequency, especially if they indicate that there may be greater risk of harm than previously recognized.

X. Definitions

Acute Respiratory Illness/infection (ARI): We will use the CDC definition of ARI that includes disease that typically involves the airways within the nose and throat and may or may not include fever. ARI is generally defined by the presence of two or more symptoms such as fever, cough, runny nose or nasal congestion, or sore throat. ARI is more sensitive (broader) than ILI to describe illness consistent with influenza because fever/feverishness are not required.

Drug eligible, influenza-infected study participant: A drug eligible study participant in the household that is diagnosed with influenza from a 98point6 provider based on a clinical review of the sick participant's symptoms.

Drug ineligible participant: A study participant in the household that is not able to receive BXM.

Influenza-like Illness in Adults and Adolescents (ILI): We will use the CDC definition of ILI that requires reported or measured fever ($>37.8^{\circ}\text{C}$) plus either cough or sore throat on one or more days preceding consultation with a tele-health physician.

Laboratory-confirmed influenza infection: We will use the CDC definition that is an individual who tests positive for influenza via an approved laboratory test, which will be the multiplex PCR (Cepheid) in this study.

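### The primary proportion is conditional on a positive self-test, so it is not the success rate of the whole home-based strategy, and the stated precision counts a different denominator

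*Protocol*

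**What the plan says.** **Primary outcome.** Protocol III (Primary Outcome Measures) counts in the numerator those among "the number of individuals eligible to receive BXM with both self-test positive influenza and laboratory-confirmed influenza" who report taking the drug within 48 hours of onset. That count is "divided by the total number of drug eligible individuals with both self-test positive influenza and laboratory-confirmed influenza". Laboratory confirmation, in Protocol X, means a person who "tests positive for influenza via an approved laboratory test, which will be the multiplex PCR (Cepheid) in this study".

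**What decides treatment.** Protocol II has the telehealth provider "provide an influenza diagnosis based on clinical judgement". Protocol V (Onset of Symptoms, drug eligible participant) says "Qualification for receipt of study drug will be determined based on a review of medical information with the tele-health provider", and "The provider will review the participant's symptoms and determine whether influenza infection is likely to be the underlying cause of the symptoms". Protocol X defines the drug eligible, influenza-infected participant as one "diagnosed with influenza from a 98point6 provider based on a clinical review of the sick participant's symptoms". None of these makes a positive self-test a condition for the drug.

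**What is known of the self-test.** Its accuracy is an unknown to be estimated: a secondary endpoint is "Sensitivity and specificity of a self-test compared to a laboratory-based molecular influenza test". Another secondary endpoint is the share of eligible people who choose to use it. Under Protocol V the self-test is used only while symptoms have lasted less than 48 hours.

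**Other populations in use.** The Summary and the primary hypothesis refer to drug-eligible people diagnosed with influenza. Protocol XI bases precision on 63 confirmed infections. SAP B6 divides on-time starts among participants with cough and a positive self-test by participants who were influenza-free at baseline.

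**The concern.** The hypothesis is that the home-based approach gets a large percentage of drug-eligible people with diagnosed influenza treated in time. The self-test is the first step of that approach. A proportion calculated only in people for whom this step worked cannot show how the whole sequence performs.

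The people left out can be identified. Table 1 of Protocol V and Protocol VI plan a Day 0 swab for PCR from every ill group, including drug-eligible people in whom influenza is not diagnosed. A confirmed infection that the self-test missed and that went untreated is a failure that is not counted. One that the provider treated on time anyway is a success that is not counted.

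No listed endpoint explicitly gives 48-hour starts among all PCR-positive drug-eligible people. The secondary endpoint on self-reported administration within 48 hours states no denominator. The pilot could therefore end without a clear estimate of the quantity its hypothesis concerns, and with a wider interval than planned.

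**Working it through.** **1. Reproduce the plan's figure (Protocol XI).**
- Expected infections: 250 × 0.25 = 62.5, stated as 63.
- Worst-case 95% half-width: 1.96 × 0.5/√63 = 0.1235, stated as ±0.12.

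Both figures reproduce, with all 63 confirmed infections counted.

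**2. Precision under the Protocol III denominator.** Let s be the share of PCR-confirmed infections that are also self-test positive. The documents give no value, so s is an assumption. The 63 are taken as all drug eligible, as the protocol's own calculation does. Then n = 63s and the half-width is 1.96 × 0.5/√n.

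| s (assumed) | n | half-width |
|---|---|---|
| 1.0 | 63 | ±0.1235 |
| 0.9 | 57 | ±0.130 |
| 0.8 | 50 | ±0.139 |
| 0.7 | 44 | ±0.148 |
| 0.6 | 38 | ±0.159 |
| 0.5 | 32 | ±0.173 |

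Only the first row matches Protocol XI.

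**3. Effect on the estimate.** Let pTP and pFN be the on-time rates in PCR-positive people with and without a positive self-test.
- Planned proportion: pTP
- Proportion among all confirmed: s·pTP + (1 − s)·pFN
- Difference: (1 − s)(pTP − pFN)

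With pTP = 0.80 (assumed), each cell shows the all-confirmed proportion and, in brackets, planned minus all-confirmed:

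| pFN (assumed) | s = 0.8 | s = 0.5 |
|---|---|---|
| 0 | 0.64 (+0.16) | 0.40 (+0.40) |
| 0.4 | 0.72 (+0.08) | 0.60 (+0.20) |
| 0.8 | 0.80 (0) | 0.80 (0) |
| 0.9 | 0.82 (−0.02) | 0.85 (−0.05) |

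The sign depends entirely on whether pFN is below, equal to or above pTP.

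**4. The group whose direction is more certain.** A confirmed case who first acts at 48 hours or later may not self-test, so cannot be doubly positive, and has already missed the 48-hour target. For this group the on-time rate is about 0. If it made up 10% of confirmed infections (assumed) and the rest started on time at 0.80, the all-confirmed proportion would be 0.9 × 0.80 = 0.72. The planned proportion would still read 0.80.

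**The case against.** The strongest defence is that this is an openly defined conditional estimand. The outcome is described as one that uses a home test, and for a feasibility pilot the time to treatment once the pathway has detected influenza is a fair question. Self-test accuracy, self-test uptake and 48-hour delivery and administration are listed separately, so missed infections would be visible. This stands as a reason to keep the doubly positive proportion. It does not justify having it as the only primary estimate. Protocol XI sizes the study on all confirmed infections, and sensitivity alone does not give the all-confirmed rate, because pFN is also needed.

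A reader might go further and infer that the planned proportion is overstated, and by a large amount. Assuming 90% on time in doubly positive people, sensitivity of 50–80% and 10–50% on time in missed infections gives all-confirmed rates from 0.5 × 0.9 + 0.5 × 0.1 = 0.50 to 0.8 × 0.9 + 0.2 × 0.5 = 0.82, an apparent overstatement of 8 to 40 points. The documents do not support this. They supply none of the three inputs, and the range leaves out pFN near pTP. Missed infections leave both parts of the fraction. If the test truly played no part in treatment and was unrelated to timing, pFN would equal pTP and false negatives would cause no bias.

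Nor is it safe to say that the test plays no part. The Data collection section of Protocol V mentions a positive test result in the branch for diagnosed influenza, and SAP B6 labels self-test positives as the treatment group. The documents do not say whether the provider sees the result.

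It is also fair to object that a wider denominator takes in more people whose household has already received baloxavir and who cannot receive it under Protocol II and V. The present denominator shares this problem, but any replacement must deal with it.

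**Conclusion.** The point holds as one about the estimand and its precision, with the direction of bias only partly determined.

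- **Estimand.** The primary proportion is conditional on a positive self-test, while treatment follows the provider's clinical diagnosis. It is not the success rate of the strategy.
- **Bias from false negatives.** It is (1 − s)(pTP − pFN): upward if missed infections are treated on time less often than detected ones, zero if equally often, downward if more often. All three inputs are unknown.
- **Bias from late presenters.** It is upward with near certainty, because the under-48-hour condition on self-testing removes them by definition. Its size depends on how many there are, which the documents do not say.
- **Precision.** The stated 63 and ±0.12 belong to a denominator of all confirmed infections. At assumed sensitivities of 0.8 and 0.5 the denominator as written gives about ±0.139 (n about 50) and ±0.173 (n about 32). This does not depend on the direction of bias.

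**What to change.** 1. In Protocol III, make the primary denominator all drug-eligible ill participants with a PCR-positive Day 0 swab, whatever the self-test result. Count untreated and late-treated people as not on time.
2. State how people in households that have already received baloxavir are counted, for example excluded from the primary denominator and reported separately, since the protocol does not let them receive the drug. Protocol II ties this limit to receipt, and Weekly Monitoring in Protocol V to receipt and administration; the two must be reconciled so that the counting rule has one trigger.
3. Keep the doubly positive proportion as a supportive per-pathway estimate, and report on-time starts by self-test result: positive, negative, invalid, not done.
4. Align SAP B6, whose denominator is influenza-free participants at baseline, with the same definition.
5. Match the precision statement in Protocol XI to the n of the chosen denominator. With all confirmed infections it stays at 63 and ±0.1235, before any exclusion under item 2 and on the protocol's assumption that all 63 are drug eligible.
6. Record whether the provider sees the self-test result, so that the results by self-test can be interpreted.

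Cost: changes of wording in both documents. The swabs and questionnaires needed are already planned. The reported proportion may be lower, and people who do not return a swab remain unclassified, so their number should be reported.
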